1. STUDY OBJECTIVES

The purpose of this study was to assess the clinical efficacy and safety of highdose Vitamin D Supplementation (VDS) in combination with Standard Urotherapy (SU) for the treatment of Overactive Bladder (OAB) dry among pediatric patients, as compared to (1) solifenacin, a commonly utilized anticholinergic medication, combined with SU, and (2) SU alone. This study endeavors to contribute to the current understanding of the optimal treatment approach for managing OAB dry in this population and has the potential to inform clinical decision-making and improve patient outcomes.

2. BACKGROUND AND RATIONALE

According to the International Children's Continence Society (ICCS), OAB is a syndrome that manifests as urinary urgency, frequently accompanied by frequency and nocturia, with or without urgency urinary incontinence, in the absence of urinary tract infection or any other obvious pathology¹. This common and concerning condition can affect individuals of all ages². Approximately, OAB has been identified with a prevalence of 5-12% in children aged 5-10 years and 0.5% in older adolescents aged 16-18 years¹. OAB may manifest as either OAB-wet, which is characterized by urgency urinary incontinence, or OAB-dry, which is characterized by urgency without

incontinence². Furthermore, it is noteworthy that those with OAB, even without urine loss, experience a reduced quality of life (QoL) compared to those without this condition³. Studies on symptoms related to OAB have revealed that they can significantly impact patients' QoL, with OAB-dry being just as distressing as urinary incontinence. Despite extensive research, the underlying pathological mechanism is not yet fully understood, and its complex etiology has resulted in a variety of treatment options⁴. While behavioral and drug therapies are the primary treatments for OAB, they may not be fully effective in curing the condition for all patients.

The first-line treatment for OAB is SU, which comprises several essential components. These include providing patients with information and demystifying their condition, instructing them on how to resolve lower urinary tract (LUT) dysfunction, offering lifestyle advice, registering symptoms and voiding habits, and providing ongoing support and encouragement through regular follow-up sessions with the caregiver⁵. Anticholinergic medications, also known as antimuscarinics, are commonly prescribed as the first-line treatment for OAB in children who exhibit persistent symptoms despite undergoing SU. Solifenacin succinate is a medication that falls into this category and is primarily employed to alleviate symptoms of OAB, such as urinary urgency, frequency, and incontinence. Although solifenacin succinate has demonstrated efficacy in clinical studies, it may result in common adverse effects, including xerostomia, constipation, blurred vision, and headache^{6,7}. These side effects may pose a challenge to patients' adherence to medication, particularly during prolonged

treatment.

There are two distinct forms of vitamin D in nature: vitamin D₃ of animal origin (cholecalciferol) and vitamin D₂ of plant origin (ergocalciferol). In humans, vitamin D₃ is produced in the skin through exposure to sunlight, whereas vitamin D₂ and D₃ can be obtained from the diet, though only a small number of foods contain substantial amounts of the vitamin^{8,9}. Vitamin D₂ and D₃ are conveyed via vitamin D-binding proteins to the liver, where they are hydroxylated by vitamin D-25-hydroxylase (CYP2R1) to produce 25-hydroxyvitamin D [25(OH)D], the primary circulating vitamin D metabolite used to assess an individual's vitamin D status. 25(OH)D is then transported to the kidney, where it is hydroxylated by 25(OH)-D-1a-hydroxylase (CYP27B1) and further hydroxylated to 1,25-dihydroxy vitamin D [1,25(OH)₂D or calcitriol], the biologically active hormonal form of vitamin $D^{10,11}$. In addition to its well-established roles in bone metabolism and immune function, emerging research suggests that vitamin D status may be inversely associated with the incidence of several diseases¹²⁻¹⁴. The vitamin D receptor has been found in cell types not involved in bone metabolism, revealing its impact on diverse physiological systems^{15,16}. These findings have prompted an increase in the number of studies investigating the potential benefits of VDS, both alone and in combination with other therapies, for a variety of medical conditions. Regardless of age and geographic location, a substantial number of patients have been observed to have deficient levels of this essential micronutrient¹⁷. Evidence suggests that there is an association between vitamin D deficiency and LUTS, such as those associated with OAB disorder¹⁸. This finding opens up new possibilities for the management of OAB through VDS. Previous studies have reported that patients with OAB have lower serum vitamin D levels, and that VDS can serve as an alternative treatment option that reduces OAB-related symptoms and improves QoL in adults¹⁹⁻²¹. According to a meta-analysis and systematic review, high-dose VDS was linked with few supplement-related clinical adverse events in children between 0 to 6 years of age²². These findings suggest that VDS may be well-tolerated in young children within the dose range of 1200 to 10,000 IU/d.

3. STUDY DESIGN.

This study is conducted in the form of a prospective, observer-blind, parallel-group randomized controlled clinical trial. The study population will consist of children aged five years or older diagnosed with OAB-dry at the Children's Hospital of Chongqing Medical University, with serum vitamin D levels below 35ng/ml. We will exclude patients with other systemic organic diseases and those with poor compliance, thus representing a relatively ideal cohort. Participants will be randomly assigned to one of three intervention groups, including a group receiving a combination of high-dose vitamin D and SU, a group receiving a combination of solifenacin and SU, and a group receiving SU alone.

This design allows for a thorough evaluation of the comparative efficacy and safety of various treatment regimens while minimizing sources of bias and confusion.

The randomized controlled design provides confidence that any observed differences between groups can be directly attributed to the experimental intervention, while the observer-blind method helps eliminate observer bias in assessment and outcome evaluation.

The parallel-group design facilitates direct comparisons between the three intervention groups, generating insightful information about the relative efficacy of each regimen. The combination of high-dose vitamin D and SU represents a novel therapeutic approach. The solifenacin and SU combination group is included to investigate the effects of previously described anticholinergics agents on outcomes. The control group receiving SU alone serves as an important reference point, providing a baseline for comparisons with other intervention measures.

4. SELECTION AND ENROLLMENT OF PARTICIPANTS.

4.1 Inclusion Criteria

• Children older than 5 years of age with a diagnosis of OAB dry (do not experience incontinence yet suffer from symptoms of urgency, frequency, and nocturia) seen at the outpatient urology clinics (diagnosis follows the latest International Children's Continence Society recommendations).

• Children with a serum vitamin D level of less than 35 ng/ml as indicated by the laboratory result.

• Written informed consent was obtained from the participants and their respective guardians.

4.2 Exclusion Criteria

• Those with a comorbidity of other urological abnormalities or serious diseases

(e.g. hypospadias, cryptorchidism, posterior urethral valves, vesicoureteral reflux, neurogenic bladder, urological tumours, urinary stones, bladder and urethral injuries, etc.).

• Those with a comorbidity of neurological disorders (e.g. epilepsy, spinal cord injury, spinal cord dysplasia, spinal cord embolism syndrome, multiple sclerosis, autism spectrum disorder, etc.).

• Those with a comorbidity of severe heart disease, abnormal liver or kidney function, lung disease, skeletal deformities, severe gastrointestinal disease, or inherited metabolic disorders.

- Those with a history of gastrointestinal surgery and urinary tract surgery.
- Those with chronic constipation.

• Those taking anticonvulsant and antiepileptic drugs, hormones, antituberculosis drugs.

• Those have a previous history of hypercalcemia, hyperphosphatemia with renal rickets.

- Those have a history of hematuria and urinary tract infection within the last 1 year.
 - Those have a history of allergy or allergic disease to vitamin D preparations.
- Those Participate in other clinical studies at the time of consultation or during the follow-up of other clinical studies.
- Any condition that could cause urinary symptoms or interfere with assessment of efficacy parameters.
 - Those unwilling to participate in this study.

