5. STUDY INTERVENTIONS

5.1 Interventions, Administration, and Duration

During the eight-week treatment period, the study was divided into three intervention groups, and each patient received follow-up care from an outpatient physician every four weeks. Participants in each intervention group will be required to attend a 30-minute SU program per session.

Children assigned to the VDS+SU group will receive high-dose VDS (800 IU, three times per day) in addition to the biweekly SU course.

Children in the SOL+SU group will receive treatment with solifenacin succinate (5 mg once daily, with a maximum dose of 10 mg per day), in addition to the SU course.

Participants in the SU group only attend regular SU meetings, which provide basic information and an explanation of the disease, guidance on behavioral changes and lifestyle advice, registration of urinary habits using a bladder diary, as well as support and encouragement from caregivers.

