6.2.3 Blinding

To minimize assessment bias and ensure the integrity of the study, we will implement rigorous measures to conceal group allocation and hypotheses from outcome assessors and statisticians. We will emphasize the importance of minimizing assessment bias to assessors and regularly review the blinding status to strictly maintain blinding. In addition, the data analyst will only be allowed to review coded data with participant names replaced by numbers.

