9. STATISTICAL CONSIDERATIONS

9.1 General Design Issues

Objective: The aim of this randomized controlled trial is to examine the effectiveness and safety of high-dose VDS plus SU for managing OAB-dry symptoms in pediatric patients with low vitamin D levels (<35ng/mL).

Specific Aim 1: The main outcome is the difference in post-treatment improvement between children who receive high-dose VDS plus SU and those who receive solifenacin plus SU or SU monotherapy for OAB-dry symptoms. The study expects that high-dose VDS plus SU will lead to more improvement than SU monotherapy and solifenacin plus SU. Furthermore, SU monotherapy will result in less improvement than solifenacin plus SU.

Specific Aim 2: The secondary outcome is the safety profile of high-dose VDS plus SU for OAB-dry symptoms in pediatric patients. The study anticipates that the safety profile of high-dose VDS plus SU will be similar to that of solifenacin plus SU or SU monotherapy at follow-up.

The study design is an 8-week randomized controlled trial, and all treatments will be administered in a group setting. Pediatric patients with OAB-dry symptoms will undergo 8 weekly sessions of high-dose VDS plus SU, solifenacin plus SU, or SU monotherapy. Independent assessors will evaluate the patients before the treatment, at mid-treatment (4-week follow-up), and at the 8-week follow-up to test the expectations. To account for attention, time, and group effects, all SU sessions will be administered in a group setting.

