We also measured how much their symptoms bothered them and how their healthrelated QoL was affected by their condition using the QoL score questionnaire. The QoL score is a tool that measures how satisfied participants are with their health and well-being. We also asked participants to rate how much they improved and how satisfied they were with the treatment using validated tools. The results of our preliminary study were positive and showed that our new intervention was promising. This encouraged us to continue with our main trial and test our intervention further. We created and finalized the study protocol, which is the document that describes the details and procedures of our study. We developed all data collection tools and forms, which are the tools and documents that we use to collect and record data from participants. We obtained IRB approvals at the National Clinical Research Center for Child Health and Disease (Chongqing, China), which are approvals from a committee that oversees the ethical aspects of our study and protects the rights and welfare of participants. We offered standard training to all coordinators and interventionists, who are the people who help us run the study and deliver the intervention to participants. Our preliminary data helped us to determine how many participants we needed for our main trial.

The primary outcome in our study will be the change in median voiding frequency from enrollment to 4-week follow-up and 8-week follow-up. In our previous feasibility study, the mean number of voids per day was 16.0 (SD, 5.0) at enrollment. We used the power analysis program PASS 15.0 to estimate the sample size of this randomized controlled trial. A sample size of 87 participants per group was needed to detect a difference of 1.5 voids per day between groups at the 0.05 level of significance, achieving more than 95% power, assuming an estimated SD of 5.0 after 8 weeks of treatment. We plan to recruit 97 participants per group, anticipating a 10% follow-up attrition, to ensure adequate power for the trial, for a total of about 300 participants. Our sample size estimations are supported by our previous trial.

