9.3.2 Per protocol (PP) analysis set

For outcomes that are categorical variables, which are non-numerical and can belong to one of several groups or categories, we will use the PP analysis set, which is a subset of subjects who followed the protocol without major deviations that could affect the outcomes. The protocol is the plan or procedure that we use to conduct the study. Deviations are when subjects do not follow the protocol as expected. For example, this includes patients who used other medications that were not allowed by the protocol or who did not follow the protocol properly. We will decide who to include or exclude in the PP analysis set before we lock the database, which is when we finalize the data after checking and cleaning them.

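### Sections 4.2 and 5.1 neither exclude nor bar vitamin D supplements or anticholinergics outside the assigned arm, and 9.3.2 relies on a list of disallowed medications that is never given

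*Combined protocol and SAP*

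**What the plan says.** **Entry.** Section 4.2 has one criterion about drugs in use: "Those taking anticonvulsant and antiepileptic drugs, hormones, antituberculosis drugs". Its only mention of vitamin D is allergy to such products. Section 4.1 caps serum vitamin D at 35 ng/ml, which limits the level and not the use of supplements.

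**Treatment period.** Section 5.1 gives one arm "high-dose VDS (800 IU, three times per day" plus urotherapy and another solifenacin plus urotherapy. For the third it says: "Participants in the SU group only attend regular SU meetings". No permitted or prohibited concomitant medication is stated for any arm. Section 5.2 asks children to complete the assigned treatment without interruption and is silent about adding others.

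**Analysis sets.** Section 9.3.2 gives, as an example of a deviation that removes a child from the per-protocol (PP) set, "patients who used other medications that were not allowed by the protocol". No list or cross-reference follows. Under 9.3.1 and 9.5.1 the primary outcome, voiding frequency, is analysed by intention to treat (ITT).

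**Detection and safety.** Section 6.1 records current medications at run-in, Week 4 and Week 8. Sections 6.2.4 and 7.2 provide for serum vitamin D at follow-up, and 10.3.2 keeps a deviation log. Section 7.1 stops medication for anticholinergic symptoms and treats a serum level above 100 ng/mL as unsafe. Section 8 stops treatment for drug-related adverse effects or worsening symptoms.

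**The concern.** As written, a child already taking a vitamin D supplement or an anticholinergic meets the listed criteria and could be randomised. A child in a comparator arm could start either during the eight weeks without breaching any stated rule.

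The plan's own text makes this plausible. Blinding is there to "conceal group allocation and hypotheses from outcome assessors and statisticians"; families are not covered. Section 9.1 describes the population as "pediatric patients with low vitamin D levels (<35ng/mL"), and the level comes from a test required for entry, so a family may well act on it. Section 2 calls anticholinergics "commonly prescribed as the first-line treatment for OAB in children who exhibit persistent symptoms despite undergoing SU", which describes a child in the SU arm who is not improving.

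Two things are at stake. Outside use during the trial changes what the arms actually compare, and an ITT analysis rightly keeps it in. Separately, a child on an anticholinergic could be allocated solifenacin, a second drug of the same class, and a child on a supplement could receive a further 3 × 800 = 2,400 IU/day.

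**Working it through.** The point is about missing rules. The plan states no figure for outside use, so there is none to reproduce. The check sets the sections side by side and then works out the direction of the effect.

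**Could other text fill the gap?**

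- *Hormones, in 4.2.* Section 2 uses the hormonal label for calcitriol, the active metabolite, and describes vitamin D2 and D3 separately. The word does not plainly cover supplements and cannot cover anticholinergics.
- *The catch-all in 4.2.* It concerns conditions that cause urinary symptoms or interfere with measuring efficacy, not medications.
- *The 35 ng/ml cap.* A child can take a supplement and still be below it.
- *The word only, for the SU arm in 5.1.* It describes the allocation. It says nothing about the other two arms and does not instruct families.
- *Crossover in 9.3.1.* It is defined so that it can be analysed as randomised; it is not prohibited.
- *Medication record, serum vitamin D, deviation log.* These can show that use occurred. Serum vitamin D cannot reveal anticholinergic use. None says which medication is a deviation.

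**Which analyses use the PP set?** Section 9.5.2 uses it for perceived improvement and for satisfaction and willingness to have another therapy. Section 9.3.3 uses it for a safety sensitivity analysis. The missing list affects these and not the primary outcome.

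**Direction of the effect on the ITT contrasts.** Let v be the extra reduction in voids from vitamin D and s that from solifenacin, each over SU alone. Let e be the fraction of v that an outside user obtains, and assume effects add.

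1. *Vitamin D in a share c of the SU arm.* VDS minus SU becomes v − c·e·v = v(1 − c·e). With v > 0 and c·e between 0 and 1, this moves toward zero. With v = 0, nothing changes.
2. *Vitamin D in a share c of the solifenacin arm.* VDS minus SOL becomes (v − s) − c·e·v. If v > s, the gap shrinks and can change sign. If v < s, it moves further from zero, in favour of solifenacin.
3. *Outside anticholinergic with added reduction a, used by share p1 in the VDS arm and p2 in the SU arm.* VDS minus SU shifts by a(p1 − p2): upward if the VDS arm uses more, downward if the SU arm uses more. The contrasts with the solifenacin arm likewise depend on which arm uses more and on what a second anticholinergic adds.

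Use already present at entry is balanced across arms in expectation by randomisation. Differential uptake afterwards is not.

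**The case against.** The strongest case is that this is mainly clarification. Current medications are recorded on Days 2–8 and randomisation follows the baseline assessment, so use at entry is visible before allocation, and an investigator might invoke the catch-all to decline such a child. Section 9.3.2 also removes children whose adherence to the protocol was poor in general, and it fixes PP membership before database lock. A child in the SU arm who takes vitamin D or solifenacin could reasonably be classed there without a drug list. On safety, there is four-weekly serum testing, a 100 ng/mL limit, and stopping rules for anticholinergic symptoms and for any drug-related harm. Section 2 cites good tolerability at 1,200 to 10,000 IU/day, though from children aged 0 to 6.

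Much of this stands. The plan has real means of detection and real safeguards, and it would be wrong to say that outside use would go unnoticed or unmanaged. But these routes rest on discretion or act after the event. None tells a clinician or family that either product is not allowed, and none makes the classification consistent between children.

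A reader might infer that outside vitamin D always pulls the vitamin D contrasts toward zero. That holds for VDS against SU only. Against solifenacin it fails whenever solifenacin is the more effective drug.

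**Conclusion.** The point holds as an omission in 4.2, 5.1 and 9.3.2: the two drug treatments under test are neither excluded at entry nor barred outside the assigned arm, and the disallowed medications are not listed. The consent form was not available for review, so this concerns the protocol and SAP text only.

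The direction is known in one case: if vitamin D works, its use in the SU arm dilutes VDS against SU. In the other cases it can go either way. This reasoning assumes that effects add.

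The size is unknown. A reader might want a loss in voids per day, or a sample-size penalty set against the planned ability "to detect a difference of 1.5 voids per day between groups". The documents give no uptake rate and no effect of outside use, so any such figure would be made of assumptions, and none is offered. Nor do the documents support the inferences that the primary analysis depends on the missing list, or that the gap invalidates the trial. It is a cheap improvement worth making.

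**What to change.** 1. Add to 4.2 an exclusion for vitamin D supplement or anticholinergic use at run-in, with a washout set by the trial's clinicians, checked against the Current Medications record before randomisation.
2. State in 5.1 that neither is allowed outside the assigned arm, with the same rule in all three arms. Clinically necessary use is permitted, recorded, and kept in the ITT analysis.
3. Cite that list in 9.3.2, so that the deviation log and the PP set share one definition. This affects only the PP-based categorical outcomes and the safety sensitivity analysis.
4. Tabulate outside use by arm at Weeks 4 and 8.

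The cost is a few lines of protocol text and one table from data already collected. The downside is that some candidates are excluded or wait for a washout; the documents do not say how many.

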6.1 Schedule of Evaluations

Assessment	Enrollment: Day1	Run-in period (Day2-8)	Week 4 (Day 33- 39)	Week 8 (Day 61-67)
Informed Consent Form	\checkmark			

Efficacy and Safety of High-Dose Vitamin D Supplementation for Overactive Bladder Dry in Children: A Randomized Clinical Trial (Edition Number:3)

Demographics	\checkmark			
Medical History	\checkmark		\checkmark	\checkmark
SU	\checkmark		\checkmark	\checkmark
Bladder Diary		\checkmark	\checkmark	\checkmark
Current Medications		\checkmark	\checkmark	\checkmark
measurements of biochemistry.	\checkmark			\checkmark
measurements of hematology,	\checkmark			\checkmark
measurements of urinalysis.	\checkmark			\checkmark
Adverse Events			\checkmark	\checkmark

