6.2.1.2 Screening

Before the interventions begin, a screening assessment must be completed to determine eligibility. Medical records will be reviewed to identify patients who meet the relevant inclusion criteria and do not meet any exclusion criteria. These criteria will be confirmed at the time of enrollment through a questionnaire.

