6.2.2.2 Baseline assessment

All participants will have a 7-day run-in period during which children are asked to carefully record their OAB-dry symptoms. The purpose of this run-in period is to establish a baseline for evaluating the effect of the intervention measures investigated.

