6.2.2.3 Randomization

After completing a comprehensive baseline assessment and meeting the eligibility

criteria, eligible participants will be randomized into one of three different intervention groups. To ensure the highest standard of allocation concealment, the randomization process of this clinical trial will be executed by a designed computer program developed by a project staff member who is not involved in the execution and statistical analysis of this study. The allocation will be securely hidden in sequentially numbered sealed envelopes, which will be entrusted to an inpatient doctor who is not involved in the trial.

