6.2.4 Follow-up Visits

Patients will undergo regular follow-ups with an outpatient physician. Follow-up assessments will include measurements of urination frequency, urgency score, lower urinary tract symptom score, nocturia frequency, serum vitamin D levels, and other clinical laboratory parameters, such as hematology, biochemistry, and urinalysis.

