7.1 Specification of Safety Parameters

Participants were required to take solifenacin and high-dose VDS as part of the study. Anticholinergic side effects, including dry mouth, blurred vision, constipation, and nausea, among others, may occur due to solifenacin use. If any of these symptoms occur, the medication will be discontinued, and the participant will be removed from the study. Over-supplementation of vitamin D can lead to symptoms of vitamin D toxicity, including anorexia, nausea, diarrhea, constipation, irritability, and somnolence. Any occurrence of these adverse drug reactions or serum vitamin D levels exceeding 100 ng/mL will be evaluated as unsafe.

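### Minor patient-safety gap, cheap to close: the only calcium exclusion looks back, and no criterion ties the Day 1 biochemistry to eligibility before a child can be allocated to 2400 IU/day of vitamin D

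*Combined protocol and SAP*

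**What the plan says.** - **Exclusion.** Section 4.2 excludes "Those have a previous history of hypercalcemia, hyperphosphatemia with renal rickets". Calcium is named nowhere else in the document, and no current value or limit is given.
- **Neighbouring exclusions.** Section 4.2 also excludes abnormal kidney function, inherited metabolic disorders, urinary stones and chronic constipation, and ends with a catch-all: "Any condition that could cause urinary symptoms or interfere with assessment of efficacy parameters". Section 3 adds that patients with other systemic organic diseases are left out.
- **How eligibility is checked.** Section 6.2.1.2 uses medical records and then states: "These criteria will be confirmed at the time of enrollment through a questionnaire". The one laboratory value written as an entry criterion is serum vitamin D below 35 ng/ml (4.1).
- **Timing.** The schedule in 6.1 ticks "measurements of biochemistry" on Day 1 and at week 8, without listing analytes. Section 6.2.2.2 says "All participants will have a 7-day run-in period" (Days 2 to 8 in 6.1), and 6.2.2.3 randomizes "After completing a comprehensive baseline assessment and meeting the eligibility" criteria.
- **Treatment.** Section 5.1 gives 800 IU of vitamin D three times a day.
- **On-treatment safety.** In 7.1 the listed vitamin D toxicity symptoms count as unsafe, and so do "serum vitamin D levels exceeding 100 ng/mL will be evaluated as unsafe". Section 7.2 has a questionnaire, a physical examination and a vitamin D test every four weeks. Section 8 stops treatment for drug-related adverse effects or worsening symptoms. Section 6.2.4 lists "other clinical laboratory parameters, such as hematology, biochemistry, and urinalysis" at follow-up without naming a week.

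**The concern.** The sponsor has already judged disturbed calcium a reason not to give this supplement, since the exclusion is there. As worded it depends on someone having found the problem earlier. Record review and a questionnaire cannot reveal a raised calcium that nobody has measured. The trial draws a blood sample that could reveal it, at a time when the result could still be used, yet the plan does not connect that sample to the criterion.

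What is at stake is the safety of an individual child. A child whose calcium is already high could be started on vitamin D with no rule prompting anyone to notice. Nothing here bears on the efficacy comparison, power or error rates.

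**Working it through.** **1. Does any written rule require a current calcium value before allocation?**

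| Place | What it covers | Requires a calcium value? |
|---|---|---|
| 4.2, calcium bullet | previous history | No |
| 4.2, kidney, metabolic, stone and constipation bullets | known or symptomatic causes and consequences | No |
| 4.2, catch-all | a condition that could cause urinary symptoms or disturb efficacy assessment | No |
| Section 3 | other systemic organic diseases | No |
| 6.1, Day 1 biochemistry | sample drawn, analytes not listed | Not stated |
| 6.2.1.2 | record review and questionnaire | No |
| 6.2.2.3 | baseline done and criteria met | No, because no criterion contains one |

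The children left uncovered are those whose hypercalcemia is current, isolated, undiagnosed and asymptomatic.

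**2. Dose.** 800 IU x 3 = 2400 IU/day (5.1).

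**3. How many children?** The documents give no prevalence, so these values are assumptions. Section 9.2 plans 97 per group, and 3 x 97 = 291.

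| Assumed prevalence | Among 291 | In the vitamin D arm of 97 |
|---|---|---|
| 0.01% | 0.03 | 0.01 |
| 0.1% | 0.29 | 0.10 |
| 1% | 2.91 | 0.97 |

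**4. Time on treatment before the next biochemistry.** Assume treatment starts on Day 9, straight after the run-in.
- If the next sample is at week 8, as 6.1 shows (Days 61 to 67): 61 - 8 = 53 to 67 - 8 = 59 days.
- If 6.2.4 means week 4 as well (Days 33 to 39): 33 - 8 = 25 to 39 - 8 = 31 days.

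At 2400 IU/day these are 127,200 to 141,600 IU and 60,000 to 74,400 IU. The first range is simply the planned course taken in full. It describes exposure and does not measure risk.

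**5. Cost of a calcium check in false exclusions.** Assume 2.5% of healthy children exceed the upper calcium limit. Then 291 x 0.025 = 7.3 would have a raised first value. If a raised value is confirmed on a second sample, a healthy child is excluded only when both values exceed the 97.5th percentile. Treat the two values as bivariate normal with within-child correlation r:

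| r | Probability both are raised | False exclusions of 291 |
|---|---|---|
| 0 | 0.000625 | 0.18 |
| 0.5 | 0.00462 | 1.35 |
| 0.7 | 0.00827 | 2.41 |
| 0.9 | 0.01482 | 4.31 |
| 1 (limit, same as no repeat) | 0.025 | 7.3 |

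Against the true cases among 291 in step 3, false exclusions are larger at 0.01% prevalence for every r shown (0.18 against 0.03), at 0.1% from r = 0.5 (1.35 against 0.29), and at 1% when r is high (4.31 at 0.9 against 2.91). Only the vitamin D arm receives the drug. Measured against its 0.97 true cases at 1%, r = 0.5 already gives more false exclusions (1.35).

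**The case against.** The strongest reply is that the plan already handles this in practice. Biochemistry is taken on Day 1, a week of run-in follows, and the criteria are applied again at randomization. By then a raised Day 1 calcium could be read as history, or as a known condition under the catch-all. Laboratory values do inform eligibility: vitamin D explicitly, and kidney and liver function by their nature. The systemic-disease exclusion in Section 3 narrows the group further. The panel contents and the handling of results may sit in operating procedures that are not in the document. The dose is near the low end of the 1200 to 10,000 IU/d range that Section 2 cites as tolerated, and only children below 35 ng/ml enrol.

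Much of this stands, and it keeps the point small. None of it requires a calcium value to be obtained or reviewed. Reading a week-old result as previous history is possible, but it strains the wording and another reader need not adopt it. The catch-all is framed around urinary symptoms and efficacy assessment, not vitamin D safety. The cited tolerability evidence is for ages 0 to 6, whereas this trial enrols children older than 5, and as cited it does not address a child whose calcium is already high.

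A reader might infer that the plan knowingly admits children with hypercalcemia, or that nothing protects them once treated. The documents do not support that. A clinician is free to act on the Day 1 result, and symptoms, worsening bladder complaints or a vitamin D level above 100 ng/mL all trigger action. Nor do the IU totals show harm, since the documents give no threshold to set them against.

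**Conclusion.** The point holds as a minor patient-safety improvement. Read literally, the criteria let a child with a current, isolated, undiagnosed and asymptomatic hypercalcemia be allocated to 2400 IU/day. The only on-treatment laboratory limit is on vitamin D, and whether biochemistry is repeated before week 8 is unclear.

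The number of such children cannot be estimated from the documents and is probably near zero: 0.01 to 0.97 in the vitamin D arm across the assumed prevalences. The wording gap itself rests on the text alone. The sizes rest on the assumed prevalence, a Day 9 start, the 2.5% upper tail and the bivariate normal model.

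It would go too far to claim a bias in efficacy, a loss of power, or a demonstrated net gain from screening. The false-exclusion figures leave that last question open. The case for the change is that an exclusion the sponsor already chose should be tied to a sample the trial already takes.

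**What to change.** 1. In 4.2, reword the bullet to *current or previous hypercalcemia, or hyperphosphatemia with renal rickets*. Keeping the renal-rickets qualifier means that isolated hyperphosphatemia does not become a new exclusion.
2. In 6.1, state that the Day 1 biochemistry includes calcium.
3. In 6.2.2.3, require that result to be reviewed against 4.2 before the envelope is opened.
4. Optionally, confirm a raised calcium on a repeat sample during the 7-day run-in before excluding the child.

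The cost is protocol wording and one result check per child, since blood is already drawn on Day 1. With the optional repeat, about 7 of 291 children would need a second sample under the 2.5% assumption. The downside is a few extra screen failures: between 0.2 and 4.3 of 291 for correlations from 0 to 0.9, and up to 7.3 without a repeat. These may exceed the true cases found, and the sponsor should accept that knowingly as the price of not giving vitamin D to a child with high calcium.
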